Statistical Methodology	
Chi Square and descriptive statistics used for questionnaire responses.
 
Mann Whitney U test for dosing adjustments and time until first anticoagulation.
 
Students t test or Mann Whitney U for dosing changes required, time until therapeutic anticoagulation, and percentage of time therapeutic anticoagulated

	Concordance assessed with mixed effects model; repeated measures ANOVA and Turkey's test for multiple comparisons to analyze heparin administration. Clinical outcomes will be compared with a Chi square test. Intention to treat analysis will be used.
--	---

A Background and Rationale

Mechanical Circulatory Support

The prevalence of heart failure in the United States currently exceeds five million and continues to rise.¹ It remains the primary diagnosis in over one million hospitalizations annually, with an economic burden exceeding \$30 billion in the United States.² People with severe heart failure and symptoms at rest may be treated with mechanical circulatory support (MCS) pumps, such as a left ventricular assist device (LVAD). This pump is used as a long-term destination therapy or as a bridge to receiving a heart transplant. As the number of organ donors remains relatively fixed, and conventional medical therapies fail, MCS is increasingly utilized in this patient population with total implants approaching 2,500 per year.³

Complications of Mechanical Circulatory Support

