specialized in post-cardiothoracic surgery care noted 100% satisfaction with the utilization and implementation of our current weight-based heparin nomogram. All nurses noted that the nomogram was clear and easy to follow. Fifty-five (98.2%) nurses felt the current dosing provided in the nomogram is feasible and 53 (94.6%) stated that they follow the dosing and monitoring instructions exactly as they are written. A total of 49 (87.5%) noted that they seek clarification from a co-worker, pharmacist, nurse practitioner, or physician regarding the nomogram instructions. When asked about suggestions for improvement of the nomogram, the most common response was to create a nomogram that is more patient specific for surgical patients at a high risk of bleeding, such as patients with LVADs. These results suggest that implementing a second nomogram based on anti-Xa assay results, that mirrors the same instructions and timing of laboratory draws as the current aPTT-based nomogram, could also be feasible.

Potential Impact of VAD ANTIX

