There is much still to be learned in the understanding of bleeding and thrombosis in the perioperative period. Perioperative events can lead to a great deal of variability in pro- and anti-thrombotic hemostatic factor levels.²⁹ Therefore, the propensity for thrombosis and bleeding in individual patients is frequently unpredictable and, can change substantially over time. Opportunity for discovery is heightened for patients with LVADs, given the dearth of rigorous investigations and the unique features of the human-machine interface. With the recent reports of increasing suspected and confirmed devastating (LVAD) pump thrombosis in the early post-implant period⁴, analyses of treatment-related factors such as the method of monitoring anticoagulation are urgently needed. Recent studies in patients with LVADs have correlated factors such as international normalized ratio (INR) in the outpatient setting³⁰, medication use³¹, and elevated systolic blood pressure³² to pump thrombosis and stroke. However, the impact of monitoring IV UFH therapy with aPTT or anti-Xa in the perioperative period on pump thrombosis, stroke and bleeding remains unknown. The early risk for both bleeding and thrombosis in patients with LVADs underlines the urgency of resolving how best to monitor and achieve appropriate anticoagulation with heparin. Given the ongoing challenges with these competing complications, studying the problem in earnest, while taking into consideration perioperative events, is crucial. Clarifying which of these two monitoring approaches is superior will facilitate safer and more effective anticoagulation with heparin in patients with LVADs.

B Study Objectives

Primary Outcome:

Demonstrate the feasibility and success of implementing nomograms for heparin administration based on both aPTT measurement and anti-factor Xa activity.

Feasibility will be determined by: 1) Questionnaires evaluating the practicality and acceptability of the nomograms 2) The percentage of correct dosing adjustments made by the nursing team required to achieve first therapeutic anticoagulation according to the specified directions provided.

Success will be determined by 1) number of dosing changes required to achieve first therapeutic anticoagulation 2) time (in hours) until achievement of first therapeutic anticoagulation 3) percentage of time therapeutic anticoagulation remains after it is achieved

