“Therapeutic anticoagulation” is defined as two consecutive monitoring values within the goal range, according to assigned monitoring assay. (either two consecutive aPTT values within 60-94 seconds or two consecutive anti-Xa values within 0.3-0.7 IU/ml)

Secondary Outcomes:

Explore heparin dosing and the concordance between the aPTT and anti-factor Xa activity in this patient population.

“Concordance” is defined when simultaneously drawn aPTT values and anti-Xas values are within the goal range (aPTT within 60-94 seconds and anti-Xa within 0.3-0.7 IU/ml).

Explore clinical outcomes including pump thrombosis, gastrointestinal bleeding, neurological events such as stroke, and major bleeding in this patient population.

C Study Design

Study setting and design

VAD AntiX feasibility study will take place at Barnes-Jewish Hospital, an academic hospital in affiliation with Washington University Medical Center located in the United States. This trial has been designed in accordance with the SPIRIT (Standard Protocol Items: Recommendations for Interventional Trials) checklist³³. The VAD AntiX feasibility study will be a stratified randomized, trial with one specific aim: (1) Demonstrate the feasibility of implementing nomograms for heparin administration based on aPTT measurement as well as anti-Xa activity. This feasibility trial will be the foundation for a larger pilot trial and subsequent comparative effectiveness trial that will seek to determine the optimal monitoring method of IV UFH in the perioperative period for LVAD patients.

A heparin nomogram is a tool or table used to standardized heparin administration and dosing when heparin is administered as a continuous infusion. Dosing adjustments are prescribed in the table based on the laboratory results.

Subject Selection

All patients 18 and older undergoing HeartMate II®, HeartMate III® or HeartWare®, LVAD implantation at Barnes-Jewish Hospital, St. Louis, Missouri, USA will be eligible for enrollment in this study. This hospital is an academic medical center affiliated with Washington University School of Medicine. Patients will be recruited preoperatively and will provide written informed consent. Any patient who is unable to receive heparin [e.g. patients with heparin-induced thrombocytopenia (HIT)] or an anaphylactic allergy to heparin] will be excluded. Patients who develop HIT during the course of the study will remain enrolled and be included in the intention-to-treat analysis.

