Inclusion criteria:

All patients 18 years of age and older who are undergoing HeartMate II®, HeartMate III® or, HeartWare® LVAD implantation at Barnes Jewish Hospital, St. Louis, Missouri, USA. Legally acceptable representatives will be able to consent for trial participation.

Exclusion criteria:

Any patient who is unable to receive heparin [e.g. patients with heparin-induced thrombocytopenia (HIT)] or an anaphylactic allergy to heparin] will be excluded. Patients who develop HIT during the course of the study will remain enrolled and be included in the intention-to-treat analysis. Additional exclusions include less than 18 years of age, patients with a known hypercoagulable disorder (factor V Leiden, Antithrombin deficiency, Protein C deficiency, Protein S deficiency, Antiphospholipid antibodies, or other thrombophilia), prisoners, pregnant or lactating women. Also, excluded are patients that are recipients of additional mechanical circulatory support (including extracorporeal membrane oxygenation support, right ventricular assist device, and/or impella) during the index LVAD implantation through the end of the study period.

Recruitment and consent:

Patients will be enrolled during a preoperative clinic visit at our Center for Preoperative Assessment and Planning, from the hospital ward at Barnes-Jewish Hospital, St. Louis, Missouri prior to surgery, or a pre-operative visit at the Ventricular Assist Device Surgery Clinic. Formal consent will be obtained from all participants prior to enrollment in the study. Authorized surrogates will be able to consent for trial participation. Any subject will be free to withdraw their consent at any time.

Interventions

Patients will be randomized to either anti-Xa or aPTT nomograms when the decision is made to start anticoagulation. Patients that receive an additional pumping support device during the index surgery, but prior to randomization will be withdrawn from the study and their baseline data will be discarded. In the rare event the patient receives the assistive pumping device after the index surgery and randomization, they will be withdrawn from the study and the data collected up to that point will be retained for analysis. Consistent with our current heparin management strategy, patients in both arms will be started on a fixed heparin dose (e.g. 750units/hour) on the morning of the first post-operative day. On the second post-operative day, patients will be placed on a

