For feasibility, questionnaires completed by the nursing staff evaluating the practicality and acceptability of the nomograms will be analyzed with descriptive statistics and compared between the two groups using a Chi square test. The percentage of correct dosing adjustments made by the nursing team required to achieve first therapeutic anticoagulation will be compared between the two groups using a Mann Whitney U test. For success, the number of dosing changes required to achieve first therapeutic

anticoagulation, the time (in hours) to achievement of first therapeutic anticoagulation, and the percentage time therapeutic anticoagulation remains after it is achieved will be compared between the two groups using a Student's t-test if data is normally distributed or a Mann-Whitney U test if data is not normally distributed.

If possible based on population size, concordance between groups of aPTT and anti-factor Xa activity will be assessed with a suitable (parametric or non-parametric) mixed effects statistical model. This approach is likely to yield more accurate information than crude correlation assessments that have been used in other studies, which have not taken into account repeated measures within patients. We will use repeated measures ANOVA and Tukey's test for multiple comparisons to analyze heparin administration in the two groups. With a mixed effects model, we will compare heparin dose in the two groups, while controlling for confounders, including the effect of time on the dose of heparin administered, and assuming an autoregressive covariance structure (the nature of the correlations between measurements for the same patient), as well as a random intercept to allow for some of the effect of potential unknown confounders.

If possible based on study size, markers of gastrointestinal bleeding, major bleeding, neurologic events, and thrombotic complications will be compared with a Chi-square test. Additionally, as able, adjusted logistic regression will be used to explore risk factors for complications. We will use intent-to-treat approach in our analyses. We will also use appropriate imputation methods and test the sensitivity of our results. No imputation is planned for missing primary outcomes data.

F Data Handling and Record Keeping

Data Collection and Methods

All questionnaire's performed will be collected and responses recorded.

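### Nurse adherence is meant to show that each nomogram can be followed, but its only named analysis is a between-arm rank test, with no interval for the level in each arm

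*Combined protocol and SAP*

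**What the plan says.** Study setting and design (section C) gives one specific aim: "Demonstrate the feasibility of implementing nomograms for heparin administration based on aPTT measurement as well as anti-Xa activity". Section B names two feasibility measures: nurse questionnaires, and the percentage of correct adjustments "made by the nursing team required to achieve first therapeutic anticoagulation according to the specified directions provided". Therapeutic anticoagulation is "defined as two consecutive monitoring values within the goal range, according to assigned monitoring assay". The part of section C on clinical team training adds that the nomograms must first be shown to be easy for clinicians to follow.

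Section E states that the "percentage of correct dosing adjustments made by the nursing team required to achieve first therapeutic anticoagulation will be compared between the two groups" by Mann-Whitney U. The Synopsis says the same more briefly: "Mann Whitney U test for dosing adjustments and time until first anticoagulation". For the questionnaires, section E names descriptive statistics as well as a test; for correct adjustments it names only the test. Under Sample size there is one general line promising descriptive statistics on the study groups, with no variable, summary measure or interval. The sample is 20 patients by convenience, 10 per arm, with no power analysis.

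**The concern.** The question is absolute and applies to each arm: are the aPTT nomogram and the anti-Xa nomogram each followed well enough to use? The protocol itself argues this way in section A, where it supports feasibility with a single-group percentage from a survey of 56 nurses: "53 (94.6%) stated that they follow the dosing and monitoring instructions exactly as they are written". That figure is self-report and covers the existing aPTT nomogram only. The documents give no comparable figure for the new anti-Xa nomogram.

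A between-arm test answers another question, namely whether adherence differs. A non-significant result could be taken as showing that both nomograms work, yet it is also expected if both are followed poorly to the same degree.

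The result will be used: "This feasibility trial will be the foundation for a larger pilot trial and subsequent comparative effectiveness trial". Planning those trials needs the level of adherence on each nomogram and how precisely 10 patients per arm have fixed it.

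**Working it through.** There is no planned figure to reproduce. The 20 patients are 10 + 10, with no alpha, power or effect size behind them.

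**1. The test does not see level.** Invented per-patient percentages, 10 per arm:
- Arm A: 100, 100, 100, 100, 95, 95, 90, 90, 85, 80 (mean 93.5).
- Arm B: 100, 100, 100, 95, 95, 95, 90, 90, 85, 75 (mean 92.5).

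Counting pairs with A above B, and ties as one half, gives U = 53.5. The null mean is 10 × 10 / 2 = 50. Ties of size 7, 5, 4 and 2 give Σ(t³ − t) = 336 + 120 + 60 + 6 = 522. The variance is (100/12) × (21 − 522/380) = 163.6, so SD = 12.79. With continuity correction, z = (53.5 − 50 − 0.5)/12.79 = 0.235 and p = 0.81.

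Halving every value gives means of 46.75 and 46.25 and the same ranks, hence the same U and p.

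Simulation agrees (two-sided 0.05, 10 per arm; assumed 2 to 6 adjustments per patient and within-patient correlation, ICC, of 0 or 0.2):

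| True adherence, both arms | Rejection rate |
|---|---|
| 50% | 4-5% |
| 75% | about 4% |
| 95% | 1-4% |

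**2. What a per-arm interval would show for the endpoint as defined.** The documents give neither the number of decisions per patient nor the ICC, so both are assumed. Decisions per patient are 2 + Poisson(3), mean 5; adherence is beta-binomial with the stated ICC. For patient i with x_i correct out of m_i:
- p = Σx_i / Σm_i
- SE(p) = √[ n/(n−1) × Σ(x_i − m_i p)² ] / Σm_i
- 95% limits: logit(p) ± t(n−1) × SE(p)/[p(1−p)], transformed back; for n = 10, t(9) = 2.262.

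Median limits, 10 patients, ICC 0.1:

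| True adherence | Median 95% interval |
|---|---|
| 95% | 81-99% |
| 80% | 61-91% |
| 50% | 32-68% |

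At a true 95%, the lower limit exceeds 80% in about 70%, 55% and 51% of trials at ICC 0, 0.1 and 0.2. These shares include trials in which every decision was followed, where a plain exact binomial limit was used.

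**3. Sensitivity.** If only actual rate changes count, at an assumed 3 or so per patient, then at a true 95% and ICC 0.1 the median interval is about 74-100%. The lower limit exceeds 80% in about 30% of trials, and every decision is followed in about 27%.

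A cruder check uses exact binomial limits on an effective sample size of 10m/[1 + (m−1) × ICC]. At m = 4 and an observed 95%, it gives 83-99% for ICC 0 (effective size 40) and 78-100% for ICC 0.2 (40/1.6 = 25).

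**4. If every decision is followed.** The data then carry no information on the ICC. For 50 of 50, the exact lower limit is 0.025^(1/n): 92.9% at n = 50 (ICC 0) and 90.2% at n = 50/1.4 = 35.7 (ICC 0.1).

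**The case against.** The strongest reply is that the endpoint is itself a percentage and the plan promises descriptive statistics on the study groups, so the level in each arm will be visible beside the p-value. This largely stands. A reader might infer that adherence per arm will go unreported; the documents do not support that. What remains is that no interval is named and that a difference test is the only analysis tied to this measure.

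The questionnaires do receive descriptive statistics and are also feasibility evidence. But they are nurses' own reports, whereas this measure concerns the adjustments actually made.

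A reader might also infer that the measure stops too early, since draws continue daily after target, and that the main analysis should run to the end of heparin or day 14. The Synopsis, section B and section E all limit it to the period up to first therapeutic anticoagulation. That is a consistent choice. Extending it and scoring every no-change result would replace a primary measure, and many routine in-range mornings could dilute the active rate changes of interest.

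Nor does the point show that 20 patients is wrong. The plan calls it a convenience sample, and a study not sized for testing is better served by estimation.

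Two objections to the interval stand as limitations: it clusters by patient only, although nurses may treat several patients, and no acceptable level is set against which to read it.

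**Conclusion.** The point holds in a limited form. The aim concerns the level of adherence on each nomogram, while the named analysis responds only to a difference between them. Per-arm percentages will probably appear, but without any statement of precision.

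That the test ignores level needs no assumption. The interval widths rest on assumed decision counts and ICCs. Under those assumptions, 10 patients per arm can separate good from very poor adherence (81-99% against 32-68%), which the planned test cannot do. They cannot reliably separate 95% from 80%. This is a change the plan should make, at low cost. It does not invalidate the design.

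**What to change.** In section E and the Synopsis, for the endpoint as defined:
- Make the percentage of correct adjustments in each arm, with a 95% confidence interval, the main summary of this feasibility measure. The interval should allow for several decisions per patient and for few patients. The logit-scale cluster-robust interval with t on (scored patients − 1) degrees of freedom is one option.
- Keep the between-arm comparison as secondary or descriptive.
- If every decision in an arm is followed, state the ICC assumed for the lower limit.
- Say whether a no-change result before target counts as an adjustment. If it does not, a patient in range on the first two nomogram draws has 0/0.
- Report how many randomized patients could not be scored. Randomization is within twelve hours of ICU arrival, but the nomogram comes later (Interventions: "On the second post-operative day, patients will be placed on a" weight-based nomogram; the procedures section leaves the start to the clinical team), and patients can be withdrawn in between.
- Adherence over the whole nomogram period, including no-change results, may be added as a secondary display, not as a substitute.

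The cost is SAP wording and modest abstraction from dosing and laboratory data already collected. The optional secondary display needs somewhat more abstraction. The downside is that the intervals will look wide; that width is the precision 10 patients per arm can give.

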Anti-Xa 0.3-0.7 IU/mL	None	No change
Anti-Xa 0.71-0.80 IU/mL	None	Decrease 1 unit/kg/hour
Anti-Xa 0.81-0.99 IU/mL	Hold infusion for 30 minutes	Decrease 2 units/kg/hour
Anti-Xa greater than 0.99 IU/mL	Hold infusion for 1 hour	Decrease 3 units/kg/hour

Draw STAT anti-Xa 6 hours each rate change.
Once two consecutive anti-Xa's are therapeutic (0.3-0.7 IU/mL), then draw anti-Xa every am.
Draw CBC Express every 72 hours until heparin is discontinued.

Duration of Study:

Patients will be followed for 14 days of heparin therapy or until heparin has been discontinued (e.g. changed to bivalirudin for anticoagulation or completed a transition to warfarin) if sooner than 14 days. If the patient has not received any IV heparin for 5 consecutive days they will be considered to have failed anticoagulation and the reason noted by the clinical team for discontinuation will be recorded.

The requirement for clinical team training and feedback:

A necessary first step in embarking on this feasibility trial is to train the clinical staff in the use of algorithms for IV UFH administration postoperatively in patients following implantation of the LVAD. It is important first to show that nomograms are practical such that clinicians can easily follow them, and second that by following the nomograms the target parameters are achieved. The collaborators in this study represent the key stakeholders responsible for the management of patients with LVADs in the postoperative period. As such, there is commitment from medical, nursing and pharmacy leadership to manage heparin administration based on either the current aPTT based or the new anti-Xa based nomogram (Table 2). During the feasibility phase, all the medical and nursing staff will undergo structured training in the rationale behind and implementation of the nomograms. Structured training will take place through formal physician and nursing in-services provided by our clinical nurse specialist and clinical pharmacist specialist. The training will include background information, practical advice, mock scenarios, trouble shooting and safety tips. To assess impact, questionnaires for the nurses taking care of the study patients will be handed out by the research team on each nursing shift. The research team will collect the completed forms for input into the database.

Risks and mitigation efforts:

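### Patients who never reach therapeutic anticoagulation have no value for hours to target or for % time after it, and the proportion reaching target is not a planned measure

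*Combined protocol and SAP*

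**What the plan says.** Section B, Primary Outcome: therapeutic anticoagulation "is defined as two consecutive monitoring values within the goal range, according to assigned monitoring assay". Success is judged by three measures: the number of dosing changes to first reach that state, the hours to reach it, and the "percentage of time therapeutic anticoagulation remains after it is achieved". One of the two feasibility measures is also tied to it: "The percentage of correct dosing adjustments made by the nursing team required to achieve first therapeutic anticoagulation".

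Section E compares the number of dosing changes, "the time (in hours) to achievement of first therapeutic anticoagulation, and the percentage time therapeutic anticoagulation remains after it is achieved" by t-test or Mann-Whitney U test, depending on normality. It then says "We will use intent-to-treat approach in our analyses", adds a general sentence on suitable imputation and sensitivity checks, and closes with "No imputation is planned for missing primary outcomes data".

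Section C, Duration of Study, ends follow-up at 14 days of heparin, or earlier if heparin stops. It labels five straight days without IV heparin as an anticoagulation failure and has the reason recorded. Patients who develop HIT stay in the intention-to-treat analysis (Subject Selection; Exclusion criteria). The clinical team, the subject or the family may end participation (Risks and mitigation efforts). For patients given added pump support after randomisation, "they will be withdrawn from the study and the data collected up to that point will be retained for analysis" (Interventions). The section on team training says it is important to show, first, that the nomograms are practical, and "second that by following the nomograms the target parameters are achieved".

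**The concern.** The protocol itself provides several ways for a randomised patient not to reach target: 14 days on heparin without two consecutive in-range values, early heparin stop (including after HIT), withdrawal, or added pump support. Such a patient has no time to target and no period after target. The plan gives no value, rank or censoring rule for this case, and the planned tests need a number for each patient.

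At stake is the description of success. If slower patients are more likely to come off heparin first, dropping them shortens the reported hours most in the slower arm. If one nomogram leaves more patients short of target, the planned comparison can miss it. The measure that would show this directly, the proportion reaching target, appears in neither the synopsis, nor Section B, nor Section E. Section C (Study setting and design) calls this trial the foundation for a larger pilot and a comparative effectiveness trial, so its figures may inform their planning.

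**Working it through.** **1. The plan's own figure.** The sample is 20 patients, 10 per arm, a convenience sample with no power analysis (Section E, Sample size). There is no calculation to reproduce.

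**2. Which measures are undefined for a non-achiever.**
- Hours to target: no value and no stated rule.
- % time after target: undefined by its own wording.
- Dosing changes and % correct adjustments up to target: countable, because follow-up and withdrawal already have ends in Duration of Study and Sample size. Section E does not say that those ends apply.
- Five-day failure label: triggered by absence of heparin, not by failure to reach range on heparin. It enters no analysis in Section E.
- General imputation sentence: names no outcome or method, and the no-imputation sentence for primary outcomes follows it.

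**3. Chance that the case arises.** The documents give no non-achievement rate *p*, so it is assumed. P(at least one of 20) = 1 − (1 − *p*)^20; expected number = 20*p*.
- *p* = 5%: 1 − 0.95^20 = 64%; 1 expected
- *p* = 10%: 1 − 0.90^20 = 88%; 2 expected
- *p* = 20%: 1 − 0.80^20 = 99%; 4 expected

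**4. Effect on hours.** All inputs are assumed except the 14-day cap (336 h) and the 6-hourly draws. Times to target are lognormal, with medians 30 and 48 h and SD of log time 0.6, rounded up to the next draw. Heparin stops are uniform over the stated window, the same in both arms. A patient is an achiever if time to target is no later than the stop (400,000 simulated patients per arm; percentages rounded).

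| Heparin stops | Reach target | No value, of 20 | Mean hours, achievers | Gap | Incidence by 48 h | Gap (points) |
|---|---|---|---|---|---|---|
| none | all | 0 | 38.9 / 60.3 | 21.4 | 78.4 / 49.9% | 28.5 |
| 72–336 h | 99 / 96% | 0.4 | 38.2 / 57.0 | 18.8 | 78.4 / 49.9% | 28.5 |
| 48–168 h | 95 / 85% | 2.0 | 36.1 / 50.4 | 14.3 | 78.4 / 50.0% | 28.4 |
| 24–120 h | 83 / 65% | 5.2 | 33.0 / 44.2 | 11.2 | 72.4 / 44.3% | 28.1 |

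The achievers-only gap narrows as stops come earlier. The gap in cumulative incidence at 48 h barely moves.

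**5. Effect on the Mann-Whitney test.** Assumed: equal speed (median 36 h in both arms), random non-achievement, 10 per arm, two-sided 5% (the plan sets no level), 10,000 trials per case. Rejection rates:

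| Non-achievement by arm | Achievers only | Non-achievers ranked last |
|---|---|---|
| 15 / 15% | 4.1% | 4.5% |
| 10 / 20% | 4.3% | 5.8% |
| 0 / 20% | 4.2% | 10.7% |
| 0 / 40% | 4.4% | 33% |

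In the unequal rows the arms do differ in reaching target, and achievers-only testing does not see it. Worst rank can mislead too: with medians 30 and 48 h, if 30% of the faster arm stop for unrelated reasons, rejection is about 27% for achievers only and 6% for worst rank. A rerun of steps 3 to 5 agreed within simulation error.

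**6. Precision of the missing measure.** Exact 95% intervals: 8/10 gives 44–97%; 10/10 gives 69–100%. For 10/10 against 6/10, Fisher's exact p = 0.087.

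**The case against.** The strongest case against is one of scale. This is a 20-patient feasibility study with no power claim, so nothing confirmatory turns on these tests. Patients may be followed for 14 days of heparin, and Section F schedules research specimens on heparin days 8 and 12 for those still on the intervention. The one stop pattern above that spans that period costs about 0.4 patients and some 2 to 3 h. The larger shifts assume that all heparin has ended by day 7 or day 5, which nothing in the documents supports. The assay values are collected, so the count reaching target could be derived later. A non-achiever is also not necessarily a missing value, since a Mann-Whitney test could rank such patients last. All of this stands, and it limits the weight of the point. It does not supply a rule, and a rule chosen after seeing the data is open to selection.

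A reader might infer more than the text supports:
- That the plan restricts analysis to achievers. It never says so; for hours to target this is the consequence of what is written.
- That non-achievers leave the intention-to-treat analysis. They still contribute to heparin dose, concordance and clinical outcomes.
- That counting of dosing changes has no end. Duration of Study and Sample size supply natural ends.
- That reasons are recorded only for the five-day group. The protocol states this for that group and is silent on the others.

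**Conclusion.** The point holds as a gap in the analysis rules with a cheap remedy. Two of the three success measures have no value for a non-achiever, no rule fills the gap, and the proportion reaching target is not planned, although the protocol says that attaining the target parameters is important to show.

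The effect is nil if every patient reaches target, small at low or balanced rates, and material only if stops are early or non-achievement is high and unequal. Its size and direction in this trial are unknown, because every rate and time used above is assumed. A reader might infer that the reported difference in hours will be materially biased; the documents do not support that. The supported risk is an incomplete description of success. Severity: minor to should-fix.

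**What to change.** 1. Add as a success measure the number and percentage of randomised patients reaching therapeutic anticoagulation in each arm, with exact 95% CI, for description and planning rather than testing. List the reason for each patient who does not. This is the minimum change.
2. Summarise time to target in all randomised patients as cumulative incidence by arm. Treat permanent heparin discontinuation or death before target as competing events and day 14 as censoring, and state how withdrawals are handled. Keep a worst-rank Mann-Whitney test as a sensitivity analysis only.
3. For non-achievers, count dosing changes and % correct adjustments to the end of follow-up already set in Duration of Study and Sample size. Label % time after target as descriptive in achievers, and give the number contributing.

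The cost is SAP wording and one data field for the reason target was not reached, with no extra draws or visits. The downsides are that cumulative incidence is less simple to report than mean hours, and that proportions at 10 per arm are imprecise.
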